14.0 STATISTICAL CONSIDERATION	
15.0 PUBLICATION PLAN	
16.0 REFERENCES	

1.0 INTRODUCTION

Introductory Statement

Since abnormal brain bioenergetic function may contribute to neurodysfunction and neurodegeneration in Alzheimer's disease (AD), manipulating brain bioenergetics may affect the symptoms or alter the course of this disease. Oxaloacetate (OAA) could offer a potential approach for manipulating brain bioenergetics. There is evidence that OAA, a Krebs cycle and gluconeogenesis intermediate, enhances glycolysis flux, supports oxidative phosphorylation, and favorably modifies bioenergetics-related infrastructures. Our pre-clinical studies have also shown that OAA activates the brain's insulin signaling pathway, reduces neuroinflammation, and activates hippocampal neurogenesis [1]. Based on these preclinical findings, a phase I pharmacokinetic (PK) study in six human AD subjects (the Pharmacokinetics of Oxaloacetate Study, or POX Study; NCT02063308) was performed. The POX Study found AD subjects tolerate 100 mg BID of OAA when administered over a one month period. No adverse events were reported.

The next logical step is to conduct a combination safety and target engagement (phase Ib) study to define an OAA dose that is safe and which engages brain bioenergetic metabolism. This study, the "Trial of OAA in AD" (TOAD) trial, is designed to accomplish these goals. The TOAD trial's primary endpoint is safety, with OAA doses that have not previously been studied in human AD subjects. One of the secondary endpoints is target engagement of brain bioenergetics by OAA. The TOAD trial will use magnetic resonance spectroscopy (MRS) and fluorodeoxyglucose positron emission tomography (FDG PET) to assess brain bioenergetic target engagement. Exploratory target engagement data generated during this study will inform future study design. Another secondary endpoint is establishment of a pharmacokinetic profile of OAA at doses that have not been previously tested.

It is hypothesized that OAA, when orally ingested in adequate amounts, is safe and will alter brain bioenergetics. We further hypothesize that the doubling of the OAA dose will result in a doubling of the plasma OAA concentrations and that plasma OAA levels will correlate with our brain bioenergetics engagement outcomes (FDG PET and MRS). The following objectives are proposed to test these hypotheses.

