2.0 OBJECTIVES

Primary Objective

The primary objective of the TOAD trial is to determine the safety and tolerability of OAA at doses up to 2 g/day. A dose escalation strategy will be used, which will involve first testing a 1 g/day OAA dose (500 mg po BID) taken for 4 weeks in 15 AD subjects. If this dose proves to be safe, 2 g/day OAA (1000 mg po BID), taken for 4 weeks in 15 subjects, will be tested. As part of the safety analysis, the following measures will be obtained: pre and post-treatment vital signs, safety labs, physical and neurological examinations, and cognitive testing data. We predict both OAA treatment doses will prove to be safe and well-tolerated.

Secondary Objectives

One of the secondary, exploratory objectives will be to test whether OAA (administered at 500 mg BID or as 1000 mg BID) has an observable effect on brain bioenergetics. Enhancement of brain glucose utilization on FDG PET, and changes in brain metabolism intermediates on

MRS, will be evaluated in both the 1 g/day dose and the 2 g/day dose cohorts. FDG PET and MRS will be measured at pre-treatment (just prior to starting OAA), and at post-treatment (just prior to stopping OAA, after approximately one month of treatment). The pre and post-treatment scans will be quantitatively analyzed and compared. We predict a dose will be found at which the post-treatment FDG PET scans show increased cortical glucose utilization, and that a dose will be found at which the post-treatment MRS scans show increased lactate and possibly other metabolite changes.

Another secondary objective is to define OAA PK properties. Specifically, we will determine plasma OAA levels after 500 mg and 1000 mg doses, to determine if a maximum absorption capacity is reached with these doses. We will also test for correlations between plasma OAA levels and brain bioenergetic biomarker, as revealed by FDG PET and MRS.

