Assuming safety outcomes are met for a particular cohort, lack of change on both the MRS and FDG PET target engagement biomarkers would argue that rather than progressing to a more advanced clinical trial phase, we will need to acquire additional very-early stage test data, such as the PK of 500 mg and 1000 mg doses to see if there is a linear relationship, and ideally to test the safety of higher OAA doses. If there is a more robust degree of target engagement with 2 g/day than the 1 g/day dose, further studies will examine safety and target engagement biomarkers at doses above 2 g/day to see if the higher doses provide more robust target engagement. If equivalent target engagement biomarker changes are seen at 1 g/day and 2 g/day OAA, the 2 g/day dose will move forward in subsequent studies. Ultimately, future studies will utilize the data from the TOAD study to define a specific target engagement biomarker analysis. Specifically, if positive MRS data emerge, results from this study will inform which metabolites are informative. Positive FDG PET data will tell us which brain regions are most informative.

Pharmacokinetics (PK)

We recently conducted an OAA PK-Safety study in AD subjects (see section 8.0 Correlative Studies / Clinical Studies). To measure PK in this study, plasma was prepared and analyzed for OAA concentration using a commercially-available coupled enzyme assay kit. Our data indicate that following oral administration the Tmax for OAA occurs between 1 and 1.5 hours.

We have recently developed a liquid chromatography-tandem mass spectroscopy (LC-MS/MS) based assay for OAA quantification that will provide sensitivity greater than what can be obtained through the coupled enzyme method. For the TOAD-PK analyses, we will use the LC-MS/MS-based assay to quantify OAA across a broader range of plasma concentrations.

Study Procedures

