In each cohort (500 mg OAA bid and 1000 mg OAA bid), the participant will consume the first dose of study medication in the clinic, after having fasted for a minimum of 8 hours. Just prior to administration of this first dose, a blood PK sample (approximately 4 mL of blood) will be drawn to provide a baseline measurement. A second PK sample will be drawn at 60 minutes post ingestion and a third PK sample will be drawn at 90 minutes post ingestion. Each PK sample will immediately be placed on ice, and will be processed into plasma within 10 minutes of collection. Aliquots of plasma (approximately 0.5 mL each) will be frozen and stored at -80°C immediately until analyses. Quantitation of OAA in plasma will be performed using the LC-MC/MS based assay described above.

Procedure Timeline

The timing of study procedures/schedule of events are summarized in the STUDY CALENDAR in Section 9.0

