We recently conducted an OAA PK-safety study in AD subjects. OAA 100 mg capsules (obtained from Terra, Inc., which markets OAA as a nutritional supplement) were administered to 6 subjects recruited from the University of Kansas Alzheimer's Disease Center (KU ADC) clinical cohort. The first 100 mg capsule was administered at the University of Kansas Clinical Translational Science Award (KU CTSA) Clinical Trials Unit (CTU), and over a four hour period PK blood samples were obtained at 15, 30, or 60 minute intervals. Basic safety labs (CBC, chemistries) and cognitive tests (MMSE, ADAS-Cog) were performed. Subjects continued on 100 mg BID OAA for one month, and then returned to the CTU where blood samples were again taken for PK determinations, safety labs and cognitive tests were repeated, and a formal side effect query were completed. There were no drop-outs, pre and post treatment cognitive scores were comparable, safety labs were unremarkable, and no side effects were reported.

Further human experience data are available from the case series of Kesari. In the Kesari case series human subjects with gliomas were administered oxaloacetate at doses far greater than 500 mg BID. This case series includes 8 subjects whose single dose amount was 1000 mg and 6 subjects whose single dose amount was 2000 mg (500 mg doses were not used in this case

series). Among the subjects maintained at these high doses a single side effect was reported to be oxaloacetate-related, and included a single subject who experienced nausea on the 2000 mg dose. Neither discontinuation nor a reduction in dosage was required. Oxaloacetate was administered TID in this case series, and the mean treatment duration for the group was over 2 months. Therefore, well over 2000 doses of over 500 mg have been administered to humans without incurring a dose limiting toxicity event.

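### Samples at 60 and 90 minutes after the first dose show near-peak levels; they do not establish the promised PK profile, and a dose ratio below 2 is not by itself evidence of an absorption maximum

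*Protocol*

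**What the plan says.** **What is promised.** Protocol section 1.0 states: "Another secondary endpoint is establishment of a pharmacokinetic profile of OAA at doses that have not been previously tested". It adds a hypothesis: "We further hypothesize that the doubling of the OAA dose will result in a doubling of the plasma OAA concentrations". Section 2.0 says "Another secondary objective is to define OAA PK properties" and makes this specific as plasma levels after 500 mg and 1000 mg, in order "to determine if a maximum absorption capacity is reached with these doses".

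**What is collected.** Section 5.0, Description of Pharmacokinetic Procedures, has one fasting pre-dose sample, then "A second PK sample will be drawn at 60 minutes post ingestion and a third PK sample will be drawn at 90 minutes". The calendar in section 9.0 lists pharmacokinetic labs at Visit 2 only, so nothing is drawn later than 90 minutes after the first dose or at steady state.

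**Where the times come from.** Section 5.0, Pharmacokinetics, reports from the sponsor's earlier study in AD that "the Tmax for OAA occurs between 1 and 1.5 hours". Section 8.0 shows that this study gave 100 mg capsules to six participants and that "over a four hour period PK blood samples were obtained at 15, 30, or 60 minute intervals".

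**A further statement.** Section 5.0, Biomarker Outcomes, lists linearity of PK between 500 mg and 1000 mg among the additional early-stage data to acquire if neither imaging biomarker changes.

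**The concern.** Sections 1.0 and 2.0 claim more than the sampling can deliver. A profile normally means exposure over time, and two post-dose points 30 minutes apart do not fix one. No analysis plan can recover samples that were never drawn.

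The absorption question has a separate difficulty. If 1000 mg gives less than twice the level of 500 mg at 60 and 90 minutes, less drug may have been absorbed, or the same amount may have been absorbed more slowly. With nothing after 90 minutes these are hard to tell apart.

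The protocol gives three reasons not to take equal timing for granted. The Tmax was observed at a dose 5 to 10 times lower. It was measured with a coupled enzyme assay that this trial replaces with LC-MS/MS. And the cohorts take different capsules (section 7.0): two of 250 mg against two of 500 mg, the latter with added microcrystalline cellulose. At stake is what a reader of the results, or the designer of the next study, would conclude about absorption at these doses.

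**Working it through.** The protocol gives no PK sample size, precision or model parameters, so there is no stated figure to reproduce. From the protocol: doses 500 and 1000 mg, samples at 1.0 and 1.5 h, Tmax 1 to 1.5 h, 15 per cohort. Assumed: a one-compartment model with first-order absorption, elimination rate ke 0.2 to 0.5 per hour, and the variability given in step 4.

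**Step 1. Do two points fix a profile?** For a unit dose, C(t) = ka/(ka − ke) × [exp(−ke·t) − exp(−ka·t)], with t counted from the end of any lag. Scale every curve so that C = 1 at both 60 and 90 minutes. Two curves that fit exactly:
- lag 0.75 h, ka 3, ke 1.564: half-life 0.44 h, Tmax 1.20 h, Cmax 1.15, AUC 1.50
- no lag, ka 3, ke 0.086: half-life 8.05 h, Tmax 1.22 h, Cmax 1.01, AUC 12.99

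Identical data are compatible with AUCs that differ by a factor of 12.99/1.50 = 8.7. AUC, half-life and clearance are not estimable, and individual Tmax is not observed. Cmax does better: when the peak lies between the samples, it is within about 15% of the measured level.

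**Step 2. What does delay alone do to the dose ratio?** Hold the extent of absorption fixed, so that the true AUC ratio is 2.00. Set Tmax to 1.25 h at 500 mg by solving ln(ka/ke)/(ka − ke) = 1.25. Then solve again for a later Tmax at 1000 mg and form ratio = 2 × C₁₀₀₀(t)/C₅₀₀(t), both C per unit dose.

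Example with ke = 0.3: Tmax 1.25 h gives ka = 1.677 and C(1.0) = 0.6745; Tmax 2.0 h gives ka = 0.774 and C(1.0) = 0.4565. The 60-minute ratio is 2 × 0.4565/0.6745 = 1.35. At 90 minutes it is 2 × 0.5297/0.6781 = 1.56.

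| Tmax at 1000 mg | Ratio at 60 min | Ratio at 90 min | C90/C60 at 1000 mg |
|---|---|---|---|
| 1.25 h (unchanged) | 2.00 | 2.00 | 1.01 |
| 1.5 h | 1.68–1.83 | 1.79–1.92 | 1.06–1.07 |
| 2.0 h | 1.16–1.48 | 1.35–1.69 | 1.15–1.17 |

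Ranges are over ke 0.2 to 0.5. A shift to 1.5 h stays inside the protocol's own Tmax window and still lowers the ratio.

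**Step 3. Can the design detect the delay?** Partly. The last column rises when absorption is later, but would stay near 1.01 if less drug were absorbed with unchanged timing. The rise is about 5 to 7% for a shift to 1.5 h and about 14 to 16% for a shift to 2 h. The protocol gives no assay or within-participant variability against which to judge those changes.

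**Step 4. How precisely is the ratio known?** On the log scale SD = √ln(1 + CV²), and the 95% CI is the ratio multiplied and divided by exp(1.96 × SD × √(2/15)). With CV 50%, SD = 0.47 and the factor is 1.40; over CV 30 to 100% it runs from 1.23 to 1.81. These figures treat the cohorts as independent. Section 4.0 lets participants join both, so they are only indicative.

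**The case against.** The samples are placed deliberately. They bracket the protocol's own Tmax, and section 8.0 adds that in the 1968 study 200 mg by mouth raised levels at 60 minutes but not at 30. If Tmax does not change with dose, the ratio is exactly 2.00 at both times under proportionality. Section 2.0 narrows the aim to plasma levels, and the section 1.0 hypothesis concerns concentrations, not AUC. Correlation with the imaging measures needs neither half-life nor clearance. All of this stands, and it rules out three stronger readings that a reader might infer.

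- *The absorption question cannot be answered at all.* Not supported: near-peak doubling is testable, and the 90/60-minute ratio carries some information on timing.
- *The sponsor will read any ratio below 2 as saturation, or will act on it.* Not supported: the protocol states no such rule, and the dose-escalation criteria in section 5.0 do not use PK.
- *A drug with no saturation could show no increase at all.* Under this model a ratio of 0.97 needs ke = 0.75 and Tmax 2 h at 1000 mg, where ka falls to 0.31, below ke. That is an extreme assumed case, and nothing in the protocol shows that Tmax moves with dose.

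Nor do the documents show that later draws are required. The calendar makes the first dose the last Visit 2 procedure, so fasted participants would stay solely for further sampling. Sparse sampling is a defensible trade-off in a safety study.

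**Conclusion.** The point holds for the wording of the secondary endpoint. A PK profile is not obtainable from this schedule, whatever the analysis. Whether near-peak levels double is answerable; whether an absorption maximum is reached is answerable only on the condition that Tmax is the same at both doses and near the value seen at 100 mg. If that fails, delay alone produces ratios of about 1.7 to 1.9 (Tmax 1.5 h) or about 1.2 to 1.7 (Tmax 2 h) although AUC is fully proportional. The sizes rest on the assumed one-compartment model and ke of 0.2 to 0.5 per hour; the non-estimability of AUC, half-life and clearance holds across the whole set of curves that fit the two points. The primary safety objective is unaffected.

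**What to change.** In sections 1.0 and 2.0, restate the endpoint as plasma OAA at 60 and 90 minutes after the first dose, with the 1000/500 mg ratio at each time and its 95% CI. Drop the terms for a PK profile and a maximum absorption capacity, and align the reference to PK properties in section 5.0, Study Design. Report the 90/60-minute ratio by cohort as a check on absorption timing. State that a dose ratio below 2 will not by itself be read as an absorption maximum. Reconcile these sections with section 5.0, Biomarker Outcomes, so that it is clear whether linearity between 500 and 1000 mg is addressed here, as near-peak levels, or left to later work.

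The cost is wording and a narrower secondary claim; no visit or sample changes. Keeping the broader claims would instead need sampling beyond 90 minutes in at least a subset, which is a matter of participant burden for the sponsor to weigh.

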6.0 EXPECTED TOXICITIES

There are no expected toxicities.

7.0 DRUG FORMULATION AND ADMINISTRATION

Drug Production Site

OAA will be purchased from Terra Biological LLC, which is based in San Diego, CA. OAA sold by Terra is produced according to good manufacturing practices.

Drug Transportation

Study medication will be shipped to the study site by express mail.

Drug Formulation

Terra markets OAA as a nutritional supplement in capsules that contain 100 mg of OAA and 150 mg of ascorbic acid. To prevent ascorbic acid from complicating interpretations, Terra will provide the study site with capsules containing 250 or 500 mg OAA and no ascorbate. This will limit the number of capsules participants must ingest.

Drug Quality Assurance

Ten of our 250 or 500 mg capsules, from the same lot being dispensed at that time, will be randomly selected each month for the duration of our study and will be analyzed according to the protocol summarized in the Table below.

Monthly analysis and quality parameters of our 250/500 mg oxaloacetate capsules.				
Method	Specification			
HPLC Oxaloacetic Acid Assay	Greater than 95%			

If the average oxaloacetate content in ten analyzed oxaloacetate capsules at any point falls below 95%, or if any other parameter does not meet our specifications, a new set of capsules will be synthesized and reanalyzed. If meeting this standard requires synthesizing a new batch of oxaloacetate, the new batch will also be fully analyzed by the protocol summarized below before being packaged into capsules. The new batch will then be dispensed to participants to ensure all participants are taking the proper dosage of oxaloacetate above 95%.

Monthly analysis and quality parameters of our 250 mg oxaloacetate capsules.				
Method	Specification			
HPLC Oxaloacetic Acid Assay	Greater than 95%			
Appearance	White to Off-White Crystalline Powder			
Sulfated Ash	Max: 0.5%			
Loss on Drying	Max: 1.0%			
Water (Karl Fisher)	Max: 1.0%			
Solution (10% in Water)	Clear			
Heavy Metals as Lead (USP <231>	Max: 0.001%			
Identification (IR)	Consistent with Structure			

Monthly analysis and quality parameters of our 500 mg oxaloacetate capsules.				
Method	Specification			
HPLC Oxaloacetic Acid Assay	Greater than 95%			
Appearance	White to Off-White Crystalline Powder			
Sulfated Ash	Max: 0.5%			
Water (Karl Fisher)	Max: 1.0%			
Heavy Metals as Lead (USP <231>	Max: 0.001%			
Identification (IR)	Consistent with Structure			

For the 500 mg capsules, microcrystalline cellulose (MC) has been added to the capsules to assist with packing the OAA in the capsules. With the 500 mg capsules, we allow for cloudiness in the solution because the presence of MC renders the solution cloudy, therefore the Solution test is not used as a parameter for the 500 mg capsules. Also with the 500 mg capsules, we will define acceptability of the capsules using the Karl Fisher test, as this test is more sensitive to water content than the Loss on Drying test. Levels less than 1.0% on the Karl Fisher test are considered acceptable.

The oxaloacetate capsules we use in these studies will be stored in plastic bottles containing a desiccant. The bottles will be kept in a locked cabinet in the KU Alzheimer's Disease Center which is monitored for temperature changes or in a secure -20 degree freezer in the University of Kansas Clinical Research Center building. Every month 10 capsules from the same lot used for dispensing will be delivered to the company that performs the analysis. The company that will perform the analysis is Expert Chemical Analysis (ECA), which is located in San Diego, CA. ECA is registered and audited by the FDA (www.ecalab.com). There is a possibility that loss of oxaloacetate integrity could occur as an artifact of the shipping process (when the capsules are briefly outside of our controlled environment), but this approach will ensure that the quality of the oxaloacetate distributed to our trial subjects meets or exceeds the quality of the assayed oxaloacetate capsules.

Drug Administration

Participants in the 1 g/day dose cohort will take 2- 250 mg OAA capsules in the morning and 2-250 mg OAA capsules in the evening for approximately 4 weeks. Participants in the 2 g/day dose cohort will take 2-500 mg OAA capsules in the morning and 2-500 capsules in the evening for approximately 4 weeks.

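### The 500 mg versus 1000 mg PK comparison is aliased with capsule formulation, so a modest departure from a ratio of 2 cannot be attributed to dose

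*Protocol*

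**What the plan says.** Protocol section 1.0 hypothesises that "the doubling of the OAA dose will result in a doubling of the plasma OAA concentrations". Section 2.0 sets a secondary objective of measuring plasma levels after 500 mg and 1000 mg "to determine if a maximum absorption capacity is reached with these doses".

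Section 7.0 (Drug Administration) fixes the capsules: "Participants in the 1 g/day dose cohort will take 2- 250 mg OAA capsules in the morning", with the same again in the evening, and "Participants in the 2 g/day dose cohort will take 2-500 mg OAA capsules in the morning", likewise repeated in the evening. Section 7.0 (Drug Quality Assurance) adds: "For the 500 mg capsules, microcrystalline cellulose (MC) has been added to the capsules to assist with packing the OAA in the capsules". Because cellulose clouds the solution, "therefore the Solution test is not used as a parameter for the 500 mg capsules". The 250 mg capsule keeps that test and must give a clear solution.

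Section 5.0 (Description of Pharmacokinetic Procedures) takes PK samples around the first, fasted, in-clinic dose: pre-dose, 60 minutes and 90 minutes.

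**The concern.** Each dose level comes in its own capsule, so the 1000/500 concentration ratio measures dose and formulation jointly. A ratio below 2 could be an absorption ceiling, or slower or less complete release from the cellulose-containing capsule. A ratio of 2 could hide a partial ceiling offset by better release.

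The sampling scheme gives little protection. With two post-dose samples and no full concentration curve, the measured levels can respond to speed of absorption as well as extent. Neither quality panel in section 7.0 includes a dissolution or disintegration test, and no bridging dose is described. A statistical analysis plan cannot repair this, because the capsule supply creates the alias.

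The protocol is alert to the general issue: section 7.0 has ascorbate left out of the study capsules so that it does not complicate interpretation. It does not discuss the same question for cellulose.

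**Working it through.** The protocol states no power, margin or variance for the PK comparison, so there is no planned figure to reproduce. The check is whether the two effects can be separated, followed by a sensitivity range.

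**Step 1. What differs between the two PK doses (section 7.0).**

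| | 500 mg dose | 1000 mg dose |
|---|---|---|
| Capsules per intake | 2 x 250 mg | 2 x 500 mg |
| Cellulose | none (inferred) | added (stated) |
| Solution test | must be clear | not applied |

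**Step 2. Separability.** Code dose as 0/1 and added cellulose as 0/1 for 15 participants per cohort. The two columns are identical (correlation 1.0).
- Intercept, dose and formulation, two separate cohorts: rank 2 of 3 columns.
- Section 4.0 allows completers of the first cohort to join the second. If the same 15 people took both doses, 15 subject effects plus dose and formulation give rank 16 of 17. Re-enrolment does not help.
- Adding one condition that gives the 500 mg dose in the cellulose-containing capsule: rank 3 of 3.

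**Step 3. Size under an assumed shift.** Let R be the concentration from the 500 mg capsule relative to the 250 mg capsule, per mg. The documents give no value for R. Under true dose proportionality, observed ratio = 2 x R.
- R = 0.90 to 1.10: 1.8 to 2.2.
- R = 0.80 to 1.20: 1.6 to 2.4.
- With a complete ceiling (true ratio 1.0), R = 0.80 to 1.20 gives 0.8 to 1.2.

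**Step 4. Speed of absorption alone.** This is an illustrative one-compartment model with assumed elimination rate 0.5/h and Tmax 1.25 h, the middle of the 1 to 1.5 hours in section 5.0 (Pharmacokinetics). The implied absorption rate is 1.20/h. Bioavailability is unchanged and the true ratio is 2.0.

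| Absorption rate, 500 mg capsule | Ratio at 60 min | Ratio at 90 min |
|---|---|---|
| 50% slower | 1.32 | 1.50 |
| 25% slower | 1.72 | 1.82 |
| unchanged | 2.00 | 2.00 |
| 25% faster | 2.20 | 2.09 |

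**Step 5. Sampling error for comparison.** Assume a between-subject CV of 40% and 15 separate participants per cohort. Log-scale SD = sqrt(ln(1 + 0.4^2)) = 0.385. Half-width = t(0.975, 28) x 0.385 x sqrt(2/15) = 2.048 x 0.385 x 0.365 = 0.288. Factor = exp(0.288) = 1.33. The 95% interval around 2.0 is 2.0/1.33 to 2.0 x 1.33, or 1.50 to 2.67.

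**The case against.** The case on the other side is substantial, and most of it stands as a limit on the point.

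- **No documented effect.** The protocol says only that cellulose helps packing and clouds a solution. Nothing in it says that release or absorption changes. A reader might infer that the comparison is biased; the documents do not support that. They show only that bias, if present, could not be recognised. The absence of cellulose from the 250 mg capsule is itself inferred.
- **Different quality panels.** This adds little. The limits that apply to both capsules are the same, and section 7.0 explains why the Solution and Loss on Drying tests are dropped for the 500 mg capsule.
- **Sampling error is as large.** The assumed 1.6-2.4 lies inside the assumed sampling interval of 1.50-2.67. The cohorts are also sequential and non-randomised, so dose stays aliased with cohort and calendar time. One formulation would remove an avoidable alias; it would not make the test clean.
- **Sampling times.** The 60 and 90 minute samples bracket the expected Tmax, where concentration is least sensitive to small timing shifts. The pair also carries some signal about speed (1.72 against 1.82 in Step 4), though a weak one.
- **Biomarkers.** A reader might extend the point to the 1 versus 2 g/day target-engagement comparison that guides later development in section 5.0. Those scans follow about four weeks of dosing, so a difference in release speed after a first dose does not carry over. The point reaches them only if total bioavailability also differs.
- **Gross ceilings.** It would be too strong to say that no departure from 2 can be interpreted. Under a 20% shift, a complete ceiling gives 0.8-1.2, well clear of 1.6-2.4.

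None of this answers the structural fact in Step 2.

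**Conclusion.** The point holds in a limited form. Dose and capsule formulation are completely aliased in the comparison behind the dose-doubling hypothesis and the absorption-capacity objective. Neither analysis nor re-enrolment can separate them. A modest departure from 2 therefore cannot be attributed to dose, and a ratio near 2 does not exclude a partial ceiling.

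The size is unknown and may be zero. The 1.6-2.4 range rests on the assumed 10-20% shift, and the alias itself on the inference that the 250 mg capsule is cellulose-free. A ratio near 1 would still point to a ceiling unless the formulation effect were much larger than assumed.

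This is a secondary objective. The primary safety objective, the dose-limiting toxicity rules and within-cohort correlations of plasma OAA with FDG PET or MRS are unaffected. Correlations pooled across cohorts carry the same alias. The change is worth making because it is cheap and the objective is stated.

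**What to change.** Supply both cohorts, or at least the in-clinic PK dose, from one capsule formulation, with each planned dose unchanged. The 500 mg capsule can make up both PK doses.

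This needs no extra participants or visits. It has two costs. Capsule count per intake, now two in both cohorts, would become one versus two. The fallback doses in section 5.0 (250 mg BID and 375 mg BID) cannot be made from whole 500 mg capsules, so they would still need their own supply, and a comparison involving them could again mix formulations.

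If the 1 g/day cohort has already been dosed, amend the PK objective to say that:
- the 1000/500 ratio estimates the effects of dose, formulation and cohort together; and
- only a departure from 2 larger than a plausible formulation shift, for example a ratio near 1, will be read as evidence of an absorption ceiling.

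The shift regarded as plausible should be stated before the PK data are seen, because the reading depends on it: in Step 4, absorption 50% slower takes the 60-minute ratio to 1.32 with no ceiling at all. This alternative costs only a change of wording.
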